A randomized, double-blind, comparative, effectiveness and safety study of Elevi[®] vs. Hetastarch in subjects undergoing Endoscopic Mucosal Resection (EMR) of colonic lesions equal to or larger than 11mm

NCT03350217

A randomized, double-blind, comparative, effectiveness and safety study of Eleview vs. Hetastarch in subjects undergoing Endoscopic Mucosal Resection (EMR) of colonic lesions equal to or larger than 11mm

Primary Investigator:

[name],
Indiana University Hospital
Indianapolis, IN 46202

Introduction:

EMR is a technique used for the removal of flat or sessile neoplasms confined to the superficial layers of the GI tract using a snare. Injection-assisted EMR is commonly used during resections of larger flat lesions as it provides submucosal lift of polyps, adenomas, other gastrointestinal mucosal lesions or early-stage cancers prior to EMR. This has been found to minimize mechanical or electrocautery damage to the deep layers of the gastrointestinal tract wall as the injectate provides a “safety cushion” as such between the area to be removed and healthy mucosal tissue (ASGE, 2008).

Several solutions are used today for injecting lesions including saline, hyaluronic acid, and hydroxyethyl starch (Hetastarch). Saline solution has been found to dissipate within minutes, which may result in a lower quality lesion lift.

Hyaluronic acid provides a longer lift, but is expensive and is not readily available in the U.S (Hwang, 2015).

A new injectate known as Eleview has been developed for use in gastrointestinal endoscopic procedures and recently approved by the FDA. This injectate boasts a cushion of excellent height and duration through the use of an oil-in-water emulsion. However the initial cost of this material is quite high (\$80 per 10 ml). Hetastarch, which is the current injectate used by [name], is a safe and considerably inexpensive solution that provides prolonged submucosal elevation and lowers procedure times (Fasoulas, 2012). Our study will aim to compare Eleview to Hetastarch in the hopes of finding the ideal submucosal injectate. This trial will focus on polyps of size ≥ 11 mm removed by snare EMR technique. Patients with lesions deemed not suitable for EMR due to features suggestive of sub-mucosal invasion will not be included.

Injectate randomization:

Study patients will be randomly assigned to the Eleview or the Hetastarch treatment group in a 1:1 ratio. Randomization will occur at the site using envelopes provided by the Investigator. The envelopes contents will specify the treatment assignment for each patient and opened by the research team (PI will be blinded).

We will monitor the safety and effectiveness data. The appropriate solutions will be injected into the submucosal space beneath the lesion(s) to be excised before the lesion(s) is/are removed. Subjects in both groups will receive the appropriate volume of injectate deemed necessary by the PI for the individual patient.

Objectives:

Primary objectives of the study are:

- To evaluate the effectiveness of Elevive injection in comparison to Hetastarch, for EMR. Effectiveness will be evaluated by the Sydney Resection Quotient (SRQ), which is defined as the size of the polyp divided by the number of pieces resected.
- To evaluate the safety of Elevive for EMR procedures in relation to adverse events and occurrence of complications during and after the EMR procedure in comparison to Hetastarch injectate.

Secondary objectives:

- To collect other effectiveness data regarding the administration of Elevive in comparison to Hetastarch, such as injectate amount required for efficient lesion lift and complete removal.

End-points:

Primary endpoints:

- Effectiveness of Elevive in comparison to Hetastarch for EMR in terms of:
 - Sydney Resection Quotient
 - Number of subjects with *en bloc* resection of lesions.
- Safety outcomes as assessed by complications during or after the procedures including:
 - Intra-procedural bleeding (bleeding requiring therapeutic intervention during the EMR).
 - Early (<24h) and delayed ($\geq 24h$ post EMR) post-procedural bleeding (bleeding post procedure that necessitates transfusion or endoscopic hemostasis because of hematemesis or a decrease of Hgb concentration of more than 2 g/dL after EMR).
 - Perforation

- Post-Polypectomy Syndrome
- Hospital admissions for any clinically relevant complications post-procedure.

Secondary endpoints:

➤ Effectiveness of Elevi[®] compared to Hetastarch in terms of:

- Injected volume needed for initial lesion lift
- Injected volume needed for complete removal of lesion
- Number of re-injections (number of times the injection device is passed down the scope).
- Number of resected pieces
- Ease of use for polyp removal and fluid behavior combined, and rated on a 5-point scale for: very easy, easy, neutral, difficult and very difficult.
- Time (in minutes) to remove the lesion completely (measured from the first injection to final excision of the lesion), and total time of procedure.
- Need for additional treatments such as avulsion, coagulation or ablation.
- Pathological reports for negative lateral and/or deep margins (lateral margins only accurately assessed in *en bloc* resections)
- Presence and number of deep resections containing muscularis propria.
- *En-bloc* resections histologically examined for free-margins.
- Recurrent or residual neoplasia rates examined by biopsy (if applicable) at the follow-up visit.

Sample size and Statistical Analysis

At least 200 patients will be enrolled. 100 of these patients will be randomized to Elevi[®] injectate and 100 will be given the standard of care, Hetastarch injectate only. Efficacy and safety of Elevi[®] injectate has only been reviewed in one previous study. Therefore, the planned sample size was not calculated using a statistical power analysis, but was regarded as sufficient to repeat the objectives of the COSMO study (2017) and satisfy the exploratory purposes of the present study. Study personnel will carry out a simple randomization using a commonly used online generator. Randomization assignments will then be sealed until day of procedure until patient eligibility has been confirmed. The Principal Investigator will remain blinded and will perform all data analysis after completion of the study.

Data will be summarized and compared using classic descriptive statistics, i.e. mean, standard deviation, coefficient of variation (%), minimum, median and maximum values for quantitative variables, and frequencies for qualitative

variables.

The Sydney Resection Quotient will be compared between treatment groups using a Wilcoxon Rank-Sum test. The proportion of subjects with *en bloc* resection of all endoscopically visible lesions will also be compared between treatment groups using a Fisher's exact test. A nominal alpha level of 0.05 will be used for both the comparisons.

No formal comparison will be performed for the secondary endpoints.

Selection criteria

Inclusion criteria:

1. Sex and age: men and women > 18 years old
2. Subjects referred for EMR of polyps of size ≥ 11 mm
3. ASA score 1, 2 or 3.
4. Contraception: Women of childbearing potential must have a negative pregnancy test (one is provided as the standard of care) or sign a waiver. Post-menopausal women must have been in that status for at least 1 year (per standard of care).
5. Subject is willing and able to participate in the study procedures and to understand and sign the informed consent

Exclusion criteria:

1. Age: Subjects is under 18 years old
2. Consent: Vulnerable subjects including those who are unable to consent
3. Pregnancy: Pregnant or breastfeeding women
4. ASA score <3
5. Physical findings: Abnormal physical findings that may interfere with the study objectives

Excluded lesions:

- Lesions less than 11 mm in largest dimension
- Lesions involving the muscularis propria (T2 lesions)
- Ulcerated depressed lesions (Paris type III) or pathology proven invasive carcinoma
- Proven malignant disease locally advanced or with metastasis
- Active inflammatory bowel disease lesion, e.g ulcerative colitis, Crohn's disease
- 6. Endoscopic appearance of invasive malignancy
- 7. Previous partial resection or attempted resection of the lesion
- 8. Allergy: Proven or potential allergic reaction to study products or history of anaphylaxis to drugs
- 9. Severe liver disease.

10. Known or suspected gastrointestinal obstruction or perforation, active diverticulitis, toxic megacolon,
11. Inflammatory bowel disease e.g ulcerative colitis or Crohn's disease
12. Hemostasis disorders (eg Von Willebrand disease, factor V Leiden thrombophilia or haemophilia), known clotting disorder (INR>1.5).
13. Subject with any other current serious medical conditions that would increase the risks associated with taking part in the study.
14. Patients must be advised to stop anticoagulation medications prior to the procedure per local practice guidelines and should re-start as clinically indicated after the procedure.

Visit 1 will be a screening appointment where the patient will be educated about the study and the informed consent document will be completed. The patient medical history will then be recorded, as well as current medications taken. The patient will also undergo a physical exam as standard of care. This visit can be combined with *Visit 2* (Day of Procedure).

During *Visit 2*, inclusion and exclusion criteria will again be confirmed and after the lesion has been measured and found to be ≥ 11 mm and suitable for EMR, the patient will be randomized to the injectate. Polyps will be documented by photographic record prior to randomization. The injectate will be prepared out of sight from the investigator performing the EMR so that the investigator will remain blinded to the injectate. Patient vital signs including BP, HR and SpO2 will be recorded prior to, during, and after the procedure. Once the lesion has been injected, only Boston Scientific Captivator snares measuring 15-20mm will be used to resect the polyps, however additional treatment modalities required will also be recorded.

Visit 3 will consist of a follow up phone call 30 days ± 7 later. The occurrence or persistence of any adverse events will be recorded.

Data integrity and safety:

All paper charts pertaining to the patient will be kept under lock and key in coordinators office away from the endoscopy area. The data entry will be performed into an excel file which will be stored on an internal network drive with encryption and password security. Regular quality control checks of the data will be performed. Only approved personnel by the IRB will have access to the file storage. This file will also not have any identifiable information (name, DOB or

mrn). A study log with the identifiable information will be kept in a separate folder (also encrypted) to enable the investigators to assist in any research audit. No procedural data except the date of examination will be entered into this log. The data and safety will reviewed annually in addition to the continuous PI monitoring. Protocol revisions will be proposed, if needed, based on the results of the safety review including, but not limited to, stopping the randomization process.

References:

COSMO (2017). A randomized, double-blind, comparative, effectiveness and safety study of SIC 8000 in subjects undergoing Endoscopic Mucosal Resection (EMR) of colonic lesions equal to or larger than 2 cm

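### Simple randomisation gives the planned 100 patients per arm only on average; use blocks that close at patient 200, and state envelope custody in the same edit (minor)

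*Combined protocol and SAP*

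**What the plan says.** **Arm sizes.** Under Injectate randomization: "Study patients will be randomly assigned to the Eleview or the Hetastarch treatment group in a 1:1 ratio". Under Sample size and Statistical Analysis: "At least 200 patients will be enrolled. 100 of these patients will be randomized to" Eleview, and another 100 are to receive Hetastarch. That section adds that the number was not derived from a power calculation and that the study's purposes are exploratory.

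**Method.** The same section says: "Study personnel will carry out a simple randomization using a commonly used online generator". Neither it nor any other section mentions blocks, stratification or another restriction.

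**Custody.** Under Injectate randomization: "Randomization will occur at the site using envelopes provided by the Investigator". That section also has the research team open the envelopes and the principal investigator stay blinded. The sample-size section keeps the assignments sealed until the procedure day and until eligibility is confirmed. It also gives all data analysis to the blinded principal investigator.

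**Order of events.** The Visit 2 text has the lesion measured, judged suitable and photographed before randomisation. The injectate is then prepared out of the endoscopist's sight "so that the investigator will remain blinded to the injectate".

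**The concern.** The plan states fixed arm sizes but chooses a method that does not fix them. Simple randomisation is an independent coin toss for each patient, so its arm sizes vary by chance. A team following the text would probably finish 200 patients with unequal arms, or would have to keep recruiting until the smaller arm reached 100. What is at stake is delivery of the stated design and a little precision.

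The second, smaller matter is custody. The capitalised Investigator supplies the envelopes, study personnel randomise, and the sealing is described in the passive voice. The text does not say who fills, seals or holds the envelopes, or whether they are opaque and numbered. The investigator performing the EMR has to stay blinded, and the principal investigator has to stay blinded and analyse the data. The custodian should therefore be named.

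**Working it through.** **Inputs.** From Injectate randomization: a 1:1 ratio. From Sample size and Statistical Analysis: at least 200 patients, 100 and 100, simple randomisation. Assumption for the check: enrolment stops at exactly N = 200.

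**The plan's own figure.** Under simple 1:1 randomisation the size of one arm is X ~ Binomial(200, 0.5). Its mean is 200 × 0.5 = 100, so 100 and 100 is the expected split. The standard deviation is √(200 × 0.5 × 0.5) = √50 = 7.07.

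**How often the split is met.**
- P(X = 100) = C(200, 100) / 2^200 = 0.0563, or 5.6%. The other 94.4% of lists miss it.
- P(X ≤ 90 or X ≥ 110) = 0.179, so a 90/110 split or worse occurs in 17.9% of lists.
- P(X ≤ 85) = 0.020 and P(X ≤ 86) = 0.028, so the 2.5% quantile is 86. By symmetry the 97.5% quantile is 114.

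**Cost of imbalance.** The variance of a difference in means is proportional to 1/n₁ + 1/n₂. Efficiency relative to equal arms is therefore 4·n₁·n₂ / N².
- 90/110: 4 × 90 × 110 / 40,000 = 0.990
- 86/114: 4 × 86 × 114 / 40,000 = 0.980

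**If recruitment continues until both arms hold at least 100.** The expected total is about 211, with a 95% chance of finishing by 229.

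**Whether varying blocks alone give 100 and 100.** They do not, because patient 200 may fall inside an open block. As an illustration, assume that blocks of 4 and 6 are equally likely. The mean block is 5 and boundaries fall on even positions, so a boundary falls at any given late even position with probability 2/5 = 0.4.
- A block closes at 200: 0.4, always balanced.
- A block of 4 starts after patient 198: 0.4 × 0.5 = 0.2. Balanced after 2 of 4: 2·2/6 = 2/3.
- A block of 6 starts after patient 198: 0.2. Balanced after 2 of 6: 3·3/15 = 0.6.
- A block of 6 starts after patient 196: 0.2. Balanced after 4 of 6: 3·3/15 = 0.6.

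The total is 0.4 + 0.133 + 0.12 + 0.12 = 0.773, so about 77% of such lists give exactly 100/100. A list constrained to close at 200 always does; for example, 20 blocks of 4 and 20 of 6 use 80 + 120 = 200 places.

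**Custody.** No arithmetic applies. Read together, the sections allow one coherent account: personnel generate and seal the list, someone called the Investigator supplies the envelopes, the research team opens them, and the endoscopist does not see the contents. The sections do not exclude an account in which the Investigator also fills or holds them.

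**The case against.** **On arm sizes.** Simple randomisation satisfies the 1:1 ratio, 100/100 is its expected result, and it is the least predictable method. The sample size is a minimum, is not based on power, and serves an exploratory purpose. Neither the Wilcoxon rank-sum test nor Fisher's exact test needs equal groups. All of this stands, and it is why the point is minor. A reader might infer that the likely imbalance biases the comparison or undermines the tests. The documents do not support that: the loss is about 2% of efficiency at the edge of the 95% range. What remains is that the text states 100 and 100 without describing anything that would produce them.

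**On predictability.** Blocks make the next assignment somewhat easier to guess. That is true, but randomly varying and undisclosed block sizes limit it, as does the endoscopist's blinding.

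**On the envelopes.** A reader might infer that the Investigator's supplying the envelopes contradicts the blinding. The documents do not show this, since a person who hands over envelopes that others filled and sealed can stay blinded. Sealing, opening by the research team and blinding of the principal investigator are all stated. Deciding suitability before the envelope is opened is the right order for concealment, and the photograph already comes before randomisation. Only the loose phrase and the unnamed custodian remain.

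**Conclusion.** The point holds at minor severity. As written, the method has a 5.6% chance of producing the stated arm sizes at 200 patients. This rests on reading the word simple literally, as independent 1:1 assignments, and on stopping at exactly 200. If the online generator was in fact set to force equal totals, the text should say so. The custody wording needs clarifying but does not prove that concealment or blinding fails, and the documents give no basis for putting a number on that risk.

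**What to change.** 1. In Sample size and Statistical Analysis, replace simple randomisation with 1:1 permuted blocks of randomly varying size, undisclosed to those who enrol patients, open envelopes or perform the EMR. State that the list is built so that a block closes at patient 200, which guarantees 100 and 100 at that point. If enrolment passes 200, the arms differ by at most half of the block in progress.
2. In Injectate randomization, remove the phrase that has the Investigator provide the envelopes. State that study personnel who do not judge eligibility, perform the EMR or analyse the data prepare and hold sequentially numbered, opaque, sealed envelopes. Use the same description in the sample-size section.

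The cost is two sentences and a new list. Study personnel already randomise and the research team already opens the envelopes, so the only possible staffing effect is naming a custodian who meets the independence condition. The downside is slightly greater predictability. If the sponsor prefers to keep simple randomisation, the minimum change is to describe 100 per arm as the expected number.

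### Injected volume is compared between arms without adjustment for lesion size, which is known before randomisation; the raw difference is unbiased but less precise than it need be.

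*Combined protocol and SAP*

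**What the plan says.** **Objective and endpoints.** Under Objectives, the secondary objective is to collect other effectiveness data, with "injectate amount required for efficient lesion lift and complete removal" given as the example. Under End-points, the secondary list opens with "Injected volume needed for initial lesion lift" and "Injected volume needed for complete removal of lesion", and goes on to re-injections, number of pieces, ease of use, removal time and others.

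**How volume is set.** Under Injectate randomization, each subject receives the "appropriate volume of injectate deemed necessary by the PI for the individual patient". Volume is therefore an outcome of the procedure and not a fixed dose.

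**Lesion size.** The Selection criteria exclude "Lesions less than 11 mm in largest dimension" and state no upper limit. The Visit 2 text places randomisation "after the lesion has been measured and found to be" at least 11 mm and suitable for EMR.

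**Allocation and analysis.** Under Sample size and Statistical Analysis, "At least 200 patients will be enrolled", 100 to each arm, by simple randomisation and without a power calculation. Quantitative variables get means, SDs, coefficients of variation, medians and ranges. Formal comparison is limited to the Sydney Resection Quotient (SRQ) and en bloc resection and is ruled out for secondary endpoints. The document mentions no covariate, no stratification by size, and no between-arm estimate or interval for volume.

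**The concern.** It is plausible, though the documents do not say so, that a larger lesion needs more fluid. If so, part of the patient-to-patient spread in volume reflects lesion size and not the injectate, and a chance difference in mean size between arms carries over into the raw difference in volume. The plan would report two means and two SDs, with no interval and no way to see how far size contributed.

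At stake is how sharply the trial can describe the difference in volume between the two fluids. The sample size rests on no precision target, so precision available at no cost in patients is worth taking. Lesion size is a proper baseline covariate because it is recorded before allocation and cannot be affected by it.

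**Working it through.** **Nothing to reproduce.** The plan states 200 patients with no effect size, SD or power, so there is no design calculation to check.

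**Inputs from the documents.** 100 patients per arm; 1:1 simple randomisation; size measured before randomisation.

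**Assumption.** The correlation r between lesion size and injected volume, on the scale modelled, is not in the documents. A range of 0.3 to 0.8 is shown.

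**Step 1: unadjusted precision.** In units of the SD of volume, SE = √(2/100) = 0.141. The 95% half-width is 1.96 × 0.141 = 0.277 SD.

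**Step 2: effect of adjustment.** Adjusting for size multiplies the SE by √(1 − r²). The share of chance variance due to size is r². The number of patients per arm that an unadjusted comparison would need for the same precision is 100 / (1 − r²).

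| r (assumed) | Share due to size | SE ratio | 95% half-width (SD) | Equivalent n per arm |
|---|---|---|---|---|
| 0 | 0% | 1.000 | 0.277 | 100 |
| 0.3 | 9% | 0.954 | 0.264 | 110 |
| 0.5 | 25% | 0.866 | 0.240 | 133 |
| 0.6 | 36% | 0.800 | 0.222 | 156 |
| 0.7 | 49% | 0.714 | 0.198 | 196 |
| 0.8 | 64% | 0.600 | 0.166 | 278 |

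The SE therefore falls by 1 − 0.954 = 4.6% at r = 0.3 and by 1 − 0.600 = 40% at r = 0.8.

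**Step 3: chance imbalance in size.** The difference in mean lesion size has the same SE, 0.141 size-SD. It exceeds 0.2 size-SD in either direction with probability 2 × [1 − Φ(0.2/0.141)] = 0.157, or about 16% of trials of this design. The resulting chance shift in the volume difference has a 95% range of ± r × 0.277 SD: ±0.083 SD at r = 0.3, ±0.139 at 0.5 and ±0.222 at 0.8.

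**Step 4: when size is the larger part.** Size accounts for half or more of the chance variance only if r² ≥ 0.5, that is, r of about 0.71 or more.

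**Step 5: simulation check.** In 4,000 simulated trials of 200 patients under simple randomisation, the ratio of adjusted to unadjusted SE was 0.868 at r = 0.5 (theory 0.866) and 0.716 at r = 0.7 (theory 0.714). With no true effect, both estimators averaged within 0.003 SD of zero, so neither is biased.

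**Illustration.** With an assumed volume SD of 10 mL, the 95% half-width is 2.8 mL unadjusted, 2.4 mL at r = 0.5 and 2.0 mL at r = 0.7.

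**The case against.** **The comparison is descriptive by design.** The study is called exploratory and secondary endpoints are deliberately left untested, so adjustment could be seen as a reviewer's preference. This stands in part: no planned test is wrong, and the gain applies to an estimate that the plan does not yet make. But ruling out a formal comparison excludes a test, not an estimate, and readers will compare the two means in any case. A 95% interval can be read as a 5% test, so it needs an exploratory label.

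**Lesion size can be tabulated by arm.** The planned summaries could show an imbalance. They would not show what it does to the volume difference.

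**The gain may be small.** This is fair. At r = 0.3 the half-width only falls from 0.277 to 0.264 SD.

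**Pieces are already scaled.** The SRQ divides polyp size by the number of pieces, so no further adjustment of pieces is asked for.

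A reader might also infer stronger points that the documents do not support:

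- *That the raw difference is confounded by size.* Randomisation keeps it unbiased.
- *That most of the difference or of the SD is due to size.* That needs r of about 0.71 or more, and no correlation is given.
- *That volume is the only secondary objective.* It is an example, and its two endpoints sit in a longer list.
- *That the trial's cost conclusion is at risk.* The Introduction says "However the initial cost of this material is quite high", but no cost objective, endpoint or analysis is planned. Converting the between-arm difference to money at the Eleview price would also charge that price for Hetastarch volume.

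**Conclusion.** The point holds as a modest matter of efficiency in an exploratory secondary analysis. The plan leaves unused a baseline value that it already collects. The potential gain is a 5% to 40% smaller standard error for the volume difference, equivalent to about 110 to 278 patients per arm instead of 100. All of this depends on an assumed size-volume correlation of 0.3 to 0.8 and on a roughly linear relation on the scale modelled. The SRQ and en bloc comparisons and the safety outcomes are unaffected.

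**What to change.** Keep the descriptive summaries and add to Sample size and Statistical Analysis:

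- For each of the two volume endpoints, an exploratory between-arm estimate with a 95% confidence interval and no test, from a regression of volume on arm and pre-randomisation lesion size. Both would be on the log scale if skewed, in which case the arm effect is a ratio of volumes.
- The same adjustment for removal time, and a count model with size as covariate for re-injections, because a linear model does not suit small counts.
- A stated unit of analysis for patients with more than one lesion. Randomisation is by patient, but the injection text allows for several lesions. Either one pre-specified lesion per patient, or all lesions with standard errors clustered by patient, would do.

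A ratio of mL to mm is not a substitute, since it removes the influence of size only if volume is proportional to size.

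The cost is a short paragraph, slightly more analysis work and some reliance on a model form. The unadjusted summaries reported alongside let readers judge that reliance. No additional data, visits or patients are needed.

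### The post-procedural bleeding definition does not count a colonic bleed treated endoscopically for rectal bleeding without transfusion or an Hgb fall above 2 g/dL

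*Combined protocol and SAP*

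**What the plan says.** The title limits the trial to "Endoscopic Mucosal Resection (EMR) of colonic lesions". Under End-points, the primary safety outcomes include two kinds of bleeding, defined in different ways:

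- Intra-procedural bleeding is "bleeding requiring therapeutic intervention during the EMR". It asks only whether an intervention was needed, with no presenting sign and no laboratory threshold.
- Post-procedural bleeding, early (under 24 hours) or delayed (24 hours or later), is bleeding that "necessitates transfusion or endoscopic hemostasis because of hematemesis or a decrease of Hgb concentration of more than 2 g/dL" after EMR.

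The list is open, introduced by "Safety outcomes as assessed by complications during or after the procedures including", and has a separate item, "Hospital admissions for any clinically relevant complications post-procedure". The primary safety objective is framed "in relation to adverse events and occurrence of complications during and after the EMR procedure".

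In Sample size and Statistical Analysis, quantitative variables get summary statistics "and frequencies for qualitative" variables. Tests are named only for the Sydney Resection Quotient and en bloc resection.

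The visit descriptions list history, medications and a physical exam (Visit 1), vital signs (Visit 2) and a phone call at 30 ± 7 days that records adverse events (Visit 3). None lists an Hgb measurement.

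**The concern.** The definition admits endoscopic hemostasis only through a trigger, and the two triggers are hematemesis and an Hgb fall above 2 g/dL. Hematemesis is an upper-GI sign, whereas every study lesion is in the colon. Rectal bleeding, hematochezia and melena appear nowhere in the document. A patient brought back and treated endoscopically for rectal bleeding may therefore fall outside the endpoint.

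No test is planned for bleeding, so the descriptive frequency is the whole result, and the definition determines it. Applied literally, the sentence can understate that frequency. Applied with informal judgment, it yields a frequency that no longer follows the written rule, and a reader cannot tell which rule was used.

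Data integrity and safety also lets the safety review lead to protocol revisions, up to stopping randomization. The document does not say which tabulations that review will use, so any effect there is conditional.

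**Working it through.** The plan gives no figure to reproduce. The check is logical: list the possible patterns and see which ones each reading of the sentence counts.

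**Inputs.** All come from the post-procedural bleeding item under End-points. T = transfusion, E = endoscopic hemostasis, H = Hgb fall above 2 g/dL. Hematemesis is taken as absent. This gives 2 × 2 × 2 = 8 patterns (T,E,H), including untreated ones. They are not assumed equally likely, so the counts below describe the rule and are not rates.

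**Step 1. The four groupings.** The sentence does not say whether the causal phrase attaches to both treatments or to hemostasis alone, or whether the Hgb fall is a cause of treatment or a criterion in its own right.

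| Reading | Rule when hematemesis is absent | Patterns counted | (0,1,0) | (1,0,0) and (1,1,0) | (0,0,1) |
|---|---|---|---|---|---|
| A: both treatments need a trigger | (T or E) and H | 3 of 8 | no | no | no |
| B: only hemostasis needs a trigger | T or (E and H) | 5 of 8 | no | yes | no |
| C: both treatments need hematemesis; an Hgb fall alone qualifies | H | 4 of 8 | no | no | yes |
| D: only hemostasis needs hematemesis; an Hgb fall alone qualifies | T or H | 6 of 8 | no | yes | yes |

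**Step 2. What no reading counts.** Six patterns involve treatment. Only (0,1,0), hemostasis without transfusion and without the Hgb fall, is treated yet uncounted under all four readings. This is the patient treated endoscopically for rectal bleeding alone.

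**Step 3. What depends on the reading.** Transfusion without the Hgb fall, (1,0,0) or (1,1,0), counts under B and D only. An untreated fall, (0,0,1), counts under C and D only. The same record can therefore be classified either way.

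**Step 4. Whether another item restores the count.** The intra-procedural item stops at the end of the EMR. The admissions item applies only to patients who are admitted. Adverse-event recording and the open list preserve the event but do not change the bleeding definition. The Hgb criterion cannot be relied on to bring in further patients, since no visit schedules the measurement.

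**Step 5. Effect of an intervention rule.** The rule T or E counts 6 patterns. Against each reading:

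- A: adds (0,1,0), (1,0,0) and (1,1,0), drops none; 3 + 3 = 6.
- B: adds (0,1,0), drops none; 5 + 1 = 6.
- C: adds (0,1,0), (1,0,0) and (1,1,0), drops (0,0,1); 4 + 3 − 1 = 6.
- D: adds (0,1,0), drops (0,0,1); 6 + 1 − 1 = 6.

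The reported rate can only stay the same or rise under A and B. It can move either way under C and D.

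**Step 6. Size per patient.** With 100 patients in an arm (Sample size and Statistical Analysis), one such patient with no other counted bleed changes the frequency by 1/100 = 1.0 percentage point. Assuming 0 to 3 such patients in an arm (not from the documents), the understatement is 0/100 to 3/100, that is 0 to 3.0 percentage points.

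**The case against.** The strongest reply concerns weight. The event is not lost: it falls within the safety objective, can be recorded as an adverse event at the 30-day call, fits the open complication list, and is an admission if the patient is admitted. The same wording applies to both arms, no test or alpha depends on it, and the trial says its sample size is meant to "satisfy the exploratory purposes of the present study". All of this is correct and limits the seriousness. It does not restore the early and delayed bleeding frequencies, which are named primary safety outcomes.

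The size is also open to challenge. Nothing in the documents anchors the upper value of 3 patients, and enrollment of at least 200 by simple randomization does not guarantee exactly 100 per arm. Both points stand; the range is only illustrative.

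The absence of a scheduled Hgb is a secondary argument. Values from clinical care may be available for patients who present with bleeding, and the core case has no qualifying fall in any event.

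Finally, a narrower remedy exists: add rectal bleeding as a trigger and make the grouping explicit. The core case would then count on all four readings. That would also be adequate. The intervention-based wording is preferred because it settles the presentation and the grouping of the treatments in one sentence and matches the adjacent intra-procedural item.

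**Conclusion.** The concern holds. As worded, the endpoint omits a colonic bleed treated by endoscopic hemostasis for rectal bleeding when there is no transfusion and no Hgb fall above 2 g/dL. This is so on all four readings, and no other section widens the definition. Transfusion alone and an untreated Hgb fall are each classified differently depending on the reading.

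Confidence is high on the wording. The practical effect is unknown, because the documents give neither a bleeding rate nor the frequency of any presentation. The 1.0-point unit effect rests on 100 patients per arm and on the patient having no other counted bleed. The consequence is possible under-reporting and inconsistent classification of a primary safety outcome. No bias between arms is shown, and no planned test or sample-size figure is affected. It should be corrected, but it does not undermine the design.

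**What to change.** Replace the post-procedural definition with one based on intervention, for example: *any bleeding after EMR, however it presents (including rectal bleeding), that leads to transfusion or endoscopic hemostasis; no Hgb value is required.* Keep the existing split at 24 hours.

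State whether an Hgb fall above 2 g/dL without treatment also counts. That is the sponsor's choice. If it counts, report it as a separate category, with the number of patients who have both a before and an after value.

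At the existing 30-day call, ask specifically about rectal bleeding and any resulting transfusion or endoscopy, and use the answers to classify events. This overlaps with the general adverse-event question but supplies what the definition needs.

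The cost is one endpoint sentence, one statement on untreated falls and one added question, with no new tests or visits. Rates may become less comparable with any earlier study that used the present wording, possibly including the COSMO (2017) study whose objectives this trial repeats; its definition cannot be seen here. If comparability matters, tabulate bleeding under both definitions, stating which grouping of the present sentence is used.
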